## LIST OF ABBREVIATIONS

AE	Adverse Event
ADE	Adverse Device Event
DM	Data Manager
DSMB	Data Safety Monitoring Board
eCRF	Electronic Case Report Form
FAS	Full Analysis Set
GAIS	Global Aesthetic Improvement Scale
ICH	International Conference of Harmonization
MedDRA	Medical Dictionary for Regulatory Activities
PAIS	Patient's Aesthetic Improvement Scale
PP	Per Protocol
PT	Preferred Term
SAF	Safety population
SAP	Statistical Analysis Plan
SOC	System Organ Class/Standard of Care
SOP	Standard Operating Procedure

CONFIDENTIAL Page 5 of 23

# STATISTICAL ANALYSIS PLAN TEMPLATE

Statistical Analysis Plan Version no. 1.0 – 20/03/2023 Clinical Investigation Plan Code FOLIAGE - 2022 EudraCT number NA

#### 1. VERSION HISTORY

#### 1.1 Version history of the SAP

Version Number	Summary/Reason for changes	Date issued
1.0	First version	20/03/2023

#### **1.2** Version history of the Protocol

Version Number	Date	Description
1.0	02/02/2022	First version

#### **1.3** Version history of the eCRF

Version Number	Date	Description
1.0	06/04/2022	First version in production

#### 2. INTRODUCTION

This is a monocenter, open label post-market clinical follow-up investigation.

Each subject is treated with the study device Foliage Hydrofil.

Foliage Hydrofil is a CE marked, class III, resorbable medical device (sterile, non-pyrogenic and physiological gel) to be used for the hydration of the skin and for the correction of superficial skin imperfections of the face and body and in the process of repairing the dermal tissue.

This Statistical Analysis Plan has been designed to document the planned analyses that will be included in study reports.

It has been drawn in agreement with Latis srl internal SOP, and with ICH E6 (R2)1 and E9 guidelines (www.ich.org). The content of this SAP is based on the final version 1 of the clinical investigation plan dated 02/02/2022 and is reviewed by the Sponsor and finalized before the database lock.

CONFIDENTIAL Page 6 of 23

# STATISTICAL ANALYSIS PLAN TEMPLATE

Statistical Analysis Plan Version no. 1.0 – 20/03/2023 Clinical Investigation Plan Code FOLIAGE - 2022 EudraCT number NA

#### 3. STUDY OBJECTIVES

#### **3.1** Primary Objectives

The primary objective of this clinical investigation is to evaluate and confirm the clinical performance of Foliage Hydrofil in the improvement of the skin hydration in the treated area at Day 98, from baseline.

#### **3.2** Secondary Objectives

The secondary objectives of this clinical investigation are:

- 1. to evaluate the clinical performance of Foliage Hydrofil in the improvement of the skin hydration in the treated area at Day 21 and 42, from baseline;
- 2. to evaluate the improvement of the skin texture, skin tone, smoothing of fine lines and wrinkles in the treated area at Day 21, 42 and 98, from baseline;
- 3. to evaluate the aesthetic change from baseline as judged by the Investigator at Day 21, 42 and 98;
- 4. to evaluate the aesthetic change from baseline as judged by the subject at Day 21, 42 and 98;
- 5. to evaluate the subject's satisfaction at Day 21, 42 and 98.

#### 4. STUDY METHODS

#### 4.1 Study Design

This is a monocenter, open label post-market clinical follow-up investigation.

#### 4.2 Treatment Administration

Each subject was treated with the study device.

The subject started treatment on the day (Day 1) after the first visit and received two further treatments at 3 weeks distance a part. Two months after the last treatment, a final visit has been planned to evaluate the final aesthetic result

#### 4.3 Randomization and Blinding

Not applicable: open-label clinical investigation.

#### 5. STUDY ENDPOINTS

#### **5.1** Primary Endpoints

The primary endpoint of the study is the change in skin hydration from baseline to Day 98, evaluated through corneometer skin examination.

#### **5.2** Secondary Endpoints

Performance secondary endpoints of this clinical investigation are:

• the evaluation of the skin hydration from baseline to Day 21 and 42, through corneometer examination.

CONFIDENTIAL Page 7 of 23

# STATISTICAL ANALYSIS PLAN TEMPLATE

Statistical Analysis Plan Version no. 1.0 – 20/03/2023 Clinical Investigation Plan Code FOLIAGE - 2022 EudraCT number NA

- the evaluation of the of the skin texture, skin tone, smoothing of fine lines and wrinkles from baseline in the treated area at Day 21, 42 and 98;
- the Investigator's aesthetic change assessment using the Global Aesthetic Improvement Scale (GAIS) at Day 21, 42 and 98. GAIS is a categorical scale with 5-points: worse than before treatment, no change, minimal improvement, good improvement, optimal improvement;
- the subject's aesthetic change assessment using the Patient's Aesthetic Improvement Scale (PAIS) at Day 21, 42 and 98. PAIS is a categorical scale with 5-points: worse, no change, somewhat improved, moderately improved, very much improved;
- the evaluation of the overall subject's satisfaction of the treatment at Day 21, 42 and 98, through a 5-points scale: very much satisfied, satisfied, not satisfied nor unsatisfied, unsatisfied, very unsatisfied.

#### **5.3** Safety Endpoints

Safety endpoints are the number, typology, severity of local and systemic adverse events. Particular attention will be paid to local adverse events like pain, erythema, edema, bruising.

#### 6. PLANNED ANALYSIS

#### **6.1** Interim Analysis

No interim analysis is planned.

#### **6.2** Final Analysis

Final analysis will be performed according to the protocol and to this Statistical Analysis Plan, after data cleaning operations and DB Lock will be performed.

The statistical analysis will be performed using SAS 9.4 for Windows (SAS Institute Inc., Cary, NC, USA).

#### 7. SAMPLE SIZE AND STATISTICAL POWER CONSIDERATION

It was assumed an average difference in the skin hydration evaluated through corneometer skin examination (capacitance) between baseline and Day 98 of 7.5, with a standard deviation of 8. With a statistically significant difference at an alpha = 0.05 a sample size of 20 subjects had 95% power to detect the above estimated difference Considering the above and a possible drop-out rate of 20%, 24 subjects have been recruited.

#### 8. ANALYSIS POPULATIONS

#### **8.1** Full Analysis set (FAS)

The Full Analysis set (FAS) will include all subjects of the SAF who have performed the baseline assessments and have at least one post-baseline assessment of any performance endpoint (primary or secondary).

CONFIDENTIAL Page 8 of 23

Statistical Analysis Plan Version no. 1.0 – 20/03/2023 Clinical Investigation Plan Code FOLIAGE - 2022 EudraCT number NA

#### 8.2 Per-Protocol (PP) Population

The Per Protocol analysis set (PP) will include all subjects of the FAS who also meet all inclusion/exclusion criteria and who do not have any major protocol deviation.

## **8.3** Safety Population

The Safety analysis set (SAF) population will include all subjects enrolled who sign informed consent and receive at least one administration of the investigational device.

#### 9. GENERAL ISSUES FOR STATISTICAL ANALYSIS

#### **9.1** Definitions, Derived Variables and Datasets

Variable	Type	Description
corneo_before	Continous	Visit 1 (Day 1) – Capacitance
		Visit 2 (Day $21 \pm 4$ Days) – Capacitance
		Visit 3 (Day $42 \pm 4$ Days) – Capacitance
corneo	Continous	Visit 4 (Day 98 ± 7 Days) – Capacitance
texture_before	Discrete	Visit 1 (Day 1) – Skin texture
		Visit 2 (Day $21 \pm 4$ Days) – Skin texture
		Visit 3 (Day $42 \pm 4$ Days) – Skin texture
		1 = Poor
		2 = Good
		3 = Very good
texture	Discrete	Visit 4 (Day $98 \pm 7$ Days) – Skin texture
		1 = Poor
		2 = Good
		3 = Very good
finelines_before	Discrete	Visit 1 (Day 1) – Fine lines
_		Visit 2 (Day $21 \pm 4$ Days) – Fine lines
		Visit 3 (Day $42 \pm 4$ Days) – Fine lines
		1 = Poor
		2 = Good
		3 = Very good
finelines	Discrete	Visit 4 (Day 98 ± 7 Days) – Fine lines
		1 = Poor
		2 = Good
		3 = Very good
tone before	Discrete	Visit 1 (Day 1) – Skin tone
_		Visit 2 (Day $21 \pm 4$ Days) – Skin tone

CONFIDENTIAL Page 9 of 23

Statistical Analysis Plan Version no. 1.0 – 20/03/2023 Clinical Investigation Plan Code FOLIAGE - 2022 EudraCT number NA

		,
		Visit 3 (Day $42 \pm 4$ Days) – Skin tone
		1 = Poor
		2 = Sufficient
		3 = Middle
		4 = Good
4	D'	
tone	Discrete	Visit 4 (Day $98 \pm 7$ Days) – Skin tone
		1 = Poor
		2 = Sufficient
		3 = Middle
		4 = Good
wrinkles before	Discrete	Visit 1 (Day 1) – Wrinkles
		Visit 2 (Day 21 ± 4 Days) – Wrinkles
		Visit 3 (Day $42 \pm 4$ Days) – Wrinkles
		VISIT 5 (Day 72 + 7 Days) - WITHKICS
		1 = Absent
		2 = Slight
		3 = Moderate
		4 = Severe
		5 = Extreme
wrinkles	Discrete	Visit 4 (Day 98 ± 7 Days) – Wrinkles
WITHKICS	Discrete	Visit 4 (Day 98 ± 7 Days) – Willikies
		1 = Absent
		2 = Slight
		3 = Moderate
		4 = Severe
		5 = Extreme
qsorres gais	Discrete	Visit 2 (Day 21 ± 4 Days) – Global aesthetic
qsorres_gais	Discrete	improvement scale (GAIS) by the Investigator
		Visit 3 (Day 42 ± 4 Days) – Global aesthetic
		improvement scale (GAIS) by the Investigator
		Visit 4 (Day 98 ± 7 Days) – Global aesthetic
		improvement scale (GAIS) by the Investigator
		1 = Worse than before treatment
		2 = No Change
		3 = Minimal Improved
		4 = Good Improved
		5 = Optimal Improved
qsorres pais	Discrete	Visit 2 (Day 21 ± 4 Days) – Patient's aesthetic
ησοπος_μαισ	Discitic	improvement scale (PAIS)
		Visit 3 (Day 42 ± 4 Days) – Patient's aesthetic
		improvement scale (PAIS)
		Visit 4 (Day 98 ± 7 Days) – Patient's aesthetic
		improvement scale (PAIS)

CONFIDENTIAL Page 10 of 23

# STATISTICAL ANALYSIS PLAN TEMPLATE

Statistical Analysis Plan Version no. 1.0 – 20/03/2023 Clinical Investigation Plan Code FOLIAGE - 2022 EudraCT number NA

		1 = Worse 2 = No Change 3 = Somewhat Improved 4 = Moderately Improved 5 = Very Much Improved 99 = Not done
qsorres_subjsatisf	Discrete	Visit 4 (Day 98 ± 7 Days) – Subject Overall Satisfaction  1 = Very Much Satisfied 2 = Satisfied 3 = Not satisfied nor unsatisfied 4 = Unsatisfied 5 = Very unsatisfied 99 = Not done

#### **9.1.1** Baseline Values

Data collected at Visit 1 (Day 1), before any study treatment administration, will be considered as baseline values.

#### **9.1.2** Duration of Exposure

The three-injection treatment session were scheduled at Visit 1 (Day 1), Visit 2 (Day 21  $\pm 4$  days) and Visit 3 (42  $\pm 4$  days). A Follow up visit (Visit 4) was scheduled at days 98  $\pm 7$  days.

The extent of exposure will be estimated based on the treatment duration.

#### **9.1.3** Treatment Compliance

Not applicable. The administrations of the investigational medical device were performed at the investigational site by a qualified professional experienced in administering injections, who was assure the correctness of subject compliance.

#### **9.1.4** Methods for Withdrawals and Missing Data

Missing data will not be replaced in any statistical analysis.

#### **9.2** Multicenter Studies Considerations

Not applicable; this is a single-center study.

#### **9.3** Multiple Comparisons and Multiplicity

No adjustment is needed.

#### **9.4** Data Safety Monitoring Board (DSMB)

No DSMB was established for this study.

CONFIDENTIAL Page 11 of 23

Latis Srl

Vers. No. 03, 05/02/18 (Ref. SOP No. 16)

# STATISTICAL ANALYSIS PLAN TEMPLATE

Statistical Analysis Plan Version no. 1.0 – 20/03/2023 Clinical Investigation Plan Code FOLIAGE - 2022 EudraCT number NA

#### 10. STUDY SUBJECTS

#### **10.1** Disposition of Subjects

Subjects' disposition by study visit will be described and summarized in the Table 1.1. Reasons for withdrawal will be described.

#### **10.2** Protocol Deviations

Protocol deviations will be reviewed and discussed with the sponsor before the database lock. Statisticians and DM will also review protocol deviations in order to define the database lock.

Protocol deviations will be described in the Table 1.2 and in the Listing 2.

#### 11. EFFICACY ANALYSIS

#### **11.1** Analysis datasets

The analysis of safety endpoints will be performed on the SAF population. Analysis of performance endpoints will be performed on the FAS population. Additionally, analysis of primary endpoint will also be performed on the PPAS population.

## 11.2 Demographics and Baseline Characteristics

Demographic (gender, age) and baseline characteristics (medical and surgical history, skin and physical examination) will be summarized from Table 1.3 to Table 1.6 and from Listing 4.1 to Listing 4.4.

If the Safety population will be much bigger than FAS population, the analysis of demographic and baseline characteristics will be repeated on the FAS population.

The descriptive statistics will include number of observations, mean, standard deviation, median, minimum and maximum for continuous variables and number of observations and their percentages for categorical parameters.

#### 11.3 Measurements of Treatment Compliance

Not applicable.

#### **11.4** Efficacy Analysis

#### 11.4.1 Primary Efficacy Endpoints

Paired t-test, when the skin hydration is normally distributed, or the corresponding non-parametric Wilcoxon signed rank test will be used to assess a significant change in skin hydration, evaluated through corneometer skin examination (capacitance), from baseline to Day 98.

The primary endpoint will be described in the Table 2.1.1.

CONFIDENTIAL Page 12 of 23

# STATISTICAL ANALYSIS PLAN TEMPLATE

Statistical Analysis Plan Version no. 1.0 – 20/03/2023 Clinical Investigation Plan Code FOLIAGE - 2022 EudraCT number NA

#### 11.4.2 Secondary Efficacy Endpoints

Paired t-test, when the skin hydration is normally distributed, or the corresponding non-parametric Wilcoxon signed rank test will be used to assess a significant change in skin hydration, evaluated through corneometer skin examination (capacitance), from baseline to Day 21 and Day 42.

Subjects will be considered responders when skin hydration increase is at least 7,5 between baseline and Day 98 and non-responders when there is not any increase in skin hydration. The number (N) and proportion of subjects (%) for each category will be reported.

The skin texture, skin tone, smoothing of fine lines and wrinkles will be summarized at all time-points in terms of number (N) and percentage (%).

Subjects will be considered responders when Investigator's evaluation of skin texture, skin tone and smoothing of fine lines increases at least one category on the assessment scale, from baseline; otherwise, subjects will be considered non-responders.

Subjects will be considered responders when Investigator's evaluation of wrinkles decreases at least two grades on the severity rating scale, from baseline; otherwise, subjects will be considered non-responders.

Subjects whose grade on the severity rating scale of Investigator's evaluation of wrinkles decreases from 2 "Slight" to 1 "Absent" will also be considered responders.

The Global Aesthetic Improvement Scale (GAIS) filled-in by the investigator and the Patient's Aesthetic Improvement Scale (PAIS) filled-in by the subject will be summarized at all time-points in terms of number (N) and percentage (%).

The overall subject's evaluation of satisfaction with the treatment at Day 98, performed by means of the 5-item scale, will be summarized through number (N) and proportion of subjects (%) for each item.

The secondary endpoints will be described from Table 2.2.1 to Table 2.2.7.

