| Secondary study endpoints of clinical perfomance | Evaluation of the skin hydration modification from baseline to Day 21 and 42, through corneometer examination To evaluate the number of responders to Foliage Hydrofil treatment at Day 98; Evaluation of the of the skin texture, skin tone, smoothing of fine lines and wrinkles modification from baseline in the treated area at Day 21, 42 and 98; Investigator's aesthetic change assessment using the Global Aesthetic Improvement Scale (GAIS) on Day 21, 42 and 98. GAIS is a categorical scale with 5-points, from worse than before treatment to "optimal improvement"; Subject's aesthetic change assessment using the Patient's Aesthetic Improvement Scale (PAIS) on Day 21, 42 and 98. PAIS is a categorical scale with 5-points, from "worse" to "very much improved"; The overall subject's satisfaction at on the treatment at Day 21, 42 and 98, through a 5-points scale (very much satisfied, satisfied, not |
| | satisfied nor unsatisfied, unsatisfied, very unsatisfied). |
| Safety endpoints | Number, typology, severity of local and systemic adverse events. Particular attention will be paid to local adverse events like pain, erythema, edema, bruising. |
| Study Treatment | Foliage Hydrofil is a CE marked, class III, resorbable medical device (sterile, non-pyrogenic and physiological gel) to be used for the hydration of the skin and for the correction of superficial skin imperfections of the face and body and in the process of repairing the dermal tissue. The main component of Foliage Hydrofil is HA sodium salt of non-animal origin, produced by bacterial fermentation. Each subject will receive three treatments, one vial 2mL (1.6% HA formulation) each, with Foliage Hydrofil, 3 weeks apart. Foliage Hydrofil will be injected with needles 30G 4mm only. The area treated with the |

CONFIDENTIAL Page 8 of 51

| | study treatment will be the face. The device administration could be done | | |
|----------------|--|--|--|
| | after an anesthetic cream application, according to Investigator's | | |
| | judgement. | | |
| Study Duration | For each subject the clinical investigation will be of about 14 weeks (3,5 | | |
| | months). | | |
| | The enrolment period will be of 4-6 months; therefore, the overall project | | |
| | duration will be of maximum 10 months. | | |
| Number of | 24 females and males planned. | | |
| Subjects | | | |
| Target Study | Caucasian women and man of 30-55 years, with signs of skin aging in | | |

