6.4.2 Corneometer assessment

Corneometer is one of the most popular measurement instrument to reproducibly and accurately determine the hydration level of the skin surface (stratum corneum).

The corneometer indicates the hydration level of the superficial layers of the skin via measurement of skin dielectric properties.

The measurements are performed by the application of a probe to the skin surface. Upon contact, an electric field passes through the stratum corneum and the dielectric constant is obtained.

The value of the dielectric constant (in arbitrary units) is directly proportional to the level of skin hydration.

On the probe head there is a fine piece of glass to ensure that only the capacitance changes due to water content are identified. Even small changes in water can be detected. The measurement time is short at only 1 second minimising occlusion effects. The depth of the measurement is 10-20µm, therefore limited to the stratum corneum, ensuring that deeper skin layers do not influence the measurement.

The measuring surface is around 49mm², so even small areas can be accurately measured.

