7.1 Sample Size Determination

Assuming an average difference in the skin hydration evaluated through corneometer skin examination (capacitance) between baseline and Day 98 of 7.5, with a standard deviation of 8, 20 subjects will allow to appreciate this difference as statistically significant at an alpha = 0.05 and a 95% power. Considering the above and a possible drop-out rate of 20%, 24 subjects will be recruited.

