7.3.5.2 Secondary endpoints

Paired t-test, when the skin hydration is normally distributed, or the corresponding non-parametric Wilcoxon signed rank test will be used to assess a significant change in skin hydration, evaluated through corneometer skin examination (capacitance), from baseline to Day 21 and Day 42.

Subjects will be considered responders when skin hydration increase is at least 10% between baseline and Day 98 and non-responders when there is not any increase in skin hydration. The number (N) and proportion of subjects (%) for each category will be reported.

The skin texture, skin tone, smoothing of fine lines and wrinkles will be summarized at all time-points in terms of number (N) and percentage (%). Subjects will be considered responders when Investigator's evaluation of skin texture, skin tone and smoothing of fine lines increases at least one category on the assessment scale, from baseline; otherwise, subjects will be considered non-responders. Subjects will be considered responders when Investigator's evaluation of wrinkles decreases at least two grades on the severity rating scale, from baseline; otherwise, subjects will be considered non-responders. Subjects whose grade on the severity rating scale of Investigator's evaluation of wrinkles decreases from 2 "Slight" to 1 "Absent" will also be considered responders.

The Global Aesthetic Improvement Scale (GAIS) filled-in by the investigator and the Patient's Aesthetic Improvement Scale (PAIS) filled-in by the subject will be summarized at all time-points in terms of number (N) and percentage (%). Subjects will be considered responders when the evaluation increases at least one level on the categorical scale, from baseline; otherwise, subjects will be considered non-responders

CONFIDENTIAL Page 32 of 51

The overall subject's evaluation of satisfaction with the treatment at Day 98, performed by means of the 5-item scale, will be summarized through number (N) and proportion of subjects (%) for each item.

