#### 13. DEVIATIONS FROM THE PROTOCOL SPECIFIED ANALYSIS

Waiting for EC approval (more than 6 months, due to Ethics Committee organization and procedures) and therefore for the start of the study, the centre purchased a new corneometer (fitted with an integrated sensor - average 50), with a capacitance algorithm based on a different scale from the one assumed when drafting the protocol.

The scale of the new corneometer is based on lower numbers, with normal values around 50 rather than around 100.

Therefore, after discussions with [name], it was decided that for skin hydration at corneometer, the subjects can be considering responders to the treatment when skin hydration increase is at least 7,5 from baseline to Day 98, using an absolute evaluation, instead of a percentage as hypothesized in the protocol drafting phase.

About the inclusion criterion n. 4 "Corneometer Capacitance of the area treated  $\leq$  80", [name] declares that the capacitance = 45 at new corneometer can be consider equivalent to capacitance = 80 at previous corneometer.

No other changes from the details specified in the study protocol have been included in this Statistical Analysis Plan (SAP).

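### The SAP replaces the CIP's 10% hydration-responder rule with a 7.5-unit gain, gives no basis for 7.5 on the new, lower-reading corneometer, and leaves smaller gains unclassified

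*SAP*

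**What the plan says.** The CIP lists hydration response as a secondary endpoint in its synopsis: "To evaluate the number of responders to Foliage Hydrofil treatment at Day 98". The synopsis and CIP 7.3.5.2 define it: "Subjects will be considered responders when skin hydration increase is at least 10% between baseline and Day 98". A non-responder is a subject with no increase at all.

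SAP 11.4.2 keeps that non-responder definition but changes the responder side: "Subjects will be considered responders when skin hydration increase is at least 7,5 between baseline and Day 98".

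SAP 13 discloses the change. While ethics approval was pending, the centre bought a new corneometer: "The scale of the new corneometer is based on lower numbers, with normal values around 50 rather than around 100". Response is therefore to be judged "using an absolute evaluation, instead of a percentage as hypothesized in the protocol drafting phase". For inclusion criterion 4 the same section states that "capacitance = 45 at new corneometer can be consider equivalent to capacitance = 80 at previous corneometer".

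CIP 6.4.2 describes the measurement: "The value of the dielectric constant (in arbitrary units) is directly proportional to the level of skin hydration".

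The figure 7.5 appears in one other role, the planned mean change in CIP 7.1: "between baseline and Day 98 of 7.5, with a standard deviation of 8". SAP 7 repeats that mean and SD unchanged.

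**The concern.** A device that reads lower is a reason to look again at any threshold in device units. It is not by itself a reason to move from a percentage to a fixed number of units. If the two scales are proportional, a percentage carries over unchanged, and it is the absolute threshold that must shrink. SAP 13 converts the entry limit but shows no conversion, data or reference for 7.5. Because the reading is in arbitrary units, a fixed cut-off has meaning only on the device for which it was set.

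Two things are at stake. Table 2.2.3 would report a rate that is not the one the CIP defined, and a reader could not tell what a gain of 7.5 units represents on this device. In addition, a subject who gains something, but less than the cut-off, is neither responder nor non-responder, so the two reported percentages need not add to 100.

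**Working it through.** **The plan's own figure.** The documents give no derivation of the 7.5-unit cut-off, so there is none to reproduce. It equals the planning mean in CIP 7.1 and SAP 7, but no passage links the two.

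**Inputs.** CIP bar 10% (CIP 7.3.5.2). SAP bar 7.5 units (SAP 11.4.2). Entry limit 80 on the old device, 45 on the new (SAP 13). Normal about 100 on the old device, about 50 on the new (SAP 13). Planned mean 7.5, SD 8 (CIP 7.1).

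**Step 1: 7.5 units as a percentage of baseline** (7.5 / baseline).
- Old limit 80: 7.5/80 = 9.4%.
- New limit 45: 7.5/45 = 16.7%.
- New baselines of 40, 35 and 30: 18.8%, 21.4% and 25.0%.
- 7.5 units equals 10% only at a baseline of 75, which lies above the new limit.

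**Step 2: the CIP bar carried to the new scale.** At an old reading of 80, 10% is 8 old units. The two anchors give ratios 50/100 = 0.5 and 45/80 = 0.5625. A straight line through both has slope (50 − 45)/(100 − 80) = 0.25.

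| Conversion | CIP bar at old 80, in new units |
|---|---|
| Ratio 0.5 | 8 × 0.5 = 4.0 |
| Ratio 0.5625 | 8 × 0.5625 = 4.5 |
| Line, slope 0.25 | 8 × 0.25 = 2.0 |

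All three are below 7.5.

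**Step 3: does 10% on the new device match the old rule?** At 45 it is 4.5 units. That matches under the 0.5625 ratio. On the line it is 4.5/2.0 = 2.25 times the CIP bar. The anchors are rounded, so the line is not established, but neither is proportionality.

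**Step 4: illustration of response rates.** Assumptions: changes are normally distributed; baselines run from 30 to 45, where the floor of 30 is not in the documents; and the planned mean and SD scale as shown. At these baselines 10% is 3.0 to 4.5 units.

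| Scaling of mean and SD | Gain ≥ 7.5 | Gain ≥ 10% |
|---|---|---|
| × 0.5 (3.75, SD 4) | 17% | 43% to 57% |
| × 0.5625 (4.22, SD 4.5) | 23% | 48% to 61% |
| None (7.5, SD 8) | 50% | 65% to 71% |

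For example, in the first row (7.5 − 3.75)/4 = 0.94, and the upper-tail probability is 0.174. For 20 subjects, the two scaled rows give about 3 to 5 responders under the SAP rule against 9 to 12 under the 10% rule. The unscaled row gives 10 against 13 to 14.

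On the line (1.875, SD 2), a 10% rule on the new device gives about 9% to 29%. The CIP rule at the matching old baselines of 80 to 20 gives about 48% to 75%.

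**Step 5: the unclassified band,** P(0 < change < cut-off), under the same assumptions.

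| Scaling | SAP rule | 10% rule |
|---|---|---|
| × 0.5 | 65% | 25% to 40% |
| × 0.5625 | 59% | 22% to 35% |
| None | 33% | 11% to 18% |

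**The case against.** The case for leaving this alone is reasonable. SAP 13 names the trigger, the old rule and the new rule. The SAP states that it is finalised before database lock. The endpoint is a count and a percentage without a test, and the CIP's own endpoint list in 5.2 omits it. The new rule makes response harder, so it cannot flatter the device. The CIP's 10% has no stated clinical rationale either. All of this stands, and it limits the weight. It does not supply a basis for 7.5 on the new scale, and it does not place the intermediate gains.

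A reader might infer more than the documents support:

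- **That 10% is the correct rule and 7.5 the wrong one.** On the line through the SAP's own anchors, a 10% rule on the new device also misses the CIP bar. The claim of the 10% rule is that it was prespecified, not that it is known to be equivalent.
- **That 7.5 was copied from the sample-size calculation.** The match is worth raising with the sponsor, but the documents do not say the cut-off came from there.
- **That asking a subject at 45 to reach 52.5 is unreasonable because normal is about 50.** SAP 13 gives a typical value, not a ceiling.

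The unclassified band was already in the CIP. The SAP change makes it wider but did not create it.

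**Conclusion.** The point holds as a minor one. With 45 taken as the entry limit, the SAP cut-off asks every eligible subject for a gain of at least 16.7%. It is stricter than the CIP bar under the 0.5 ratio, the 0.5625 ratio and the line through both rounded anchors. No basis for 7.5 is given, and a lower-reading scale alone does not provide one. These conclusions need only the documents' own figures.

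The projected response rates and band sizes are illustrations. They rest on normal changes, a baseline floor of 30 and an assumed scaling, and they should not be read as forecasts. The primary analysis tests the change itself and does not use the cut-off, so it is unaffected.

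**What to change.** - **SAP 11.4.2 and Table 2.2.3:** report the rate under the CIP's 10% rule and the rate under the 7.5-unit rule side by side. Label the first as prespecified in the CIP and the second as changed in the SAP. Do not claim that either reproduces the rule on the old device.
- **SAP 13:** state how 7.5 was obtained for the new scale, including whether it is the planning mean, and why a percentage was not kept.
- **SAP 11.4.2:** count every gain below the cut-off as non-response, as that section already does for texture, tone, fine lines and wrinkles, or define a named intermediate category.

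The cost is SAP wording and one or two derived variables. Listing 5.1 already holds each subject's hydration value at every visit, and SAP 14 allows additional tables.
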